Method: The study will be a double-blind randomized controlled clinical trial, parallel design. A total of 50 healthy children aged 5-7 years, will be selected from Pediatric Dentistry and Dental Public Health Department, Faculty of Dentistry, Alexandria University, Egypt. Children will be selected with scores 3 or 4 Frankl behavioral rating scale. Each child selected will have at least one mandibular primary molar that is indicated for extraction. Written informed consent will be obtained from guardian. Participants will be randomly allocated into two groups according to the technique of anesthesia that will be used. Group I (test group) will receive CC-ILA, while group II (control group) will receive IANB. Heart rate will be used as vital parameter of pain, and will be recorded at base line, during injection and during extraction procedure. Pain reaction will be assessed objectively by two investigators using Sensory, Eye, Motor (SEM) scale, while subjectively the pain will be evaluated by asking the child to express his experience using a modified face scale from the Maunuksela scale.

Results: Data will be collected, tabulated and statistically analysed to obtain the results and conclusions of this study.

Keywords: Computer – controlled, Intraligamentary, Local anesthesia, Nerve block, Articaine, Pain, Extraction.

INTRODUCTION

Child management is a primary challenge facing pediatric dentists routinely. Uncooperative behaviour can significantly affect treatment quality, time, and increase the possibility of child injury during treatment as mentioned by Ingersoll and Ingersoll.⁽¹⁾ Acknowledgement of various behaviour management techniques, operating skills, and most importantly providing profound local anaesthesia are critical to deliver high quality dental service.⁽²⁾

Local anaesthetic (LA) forms the backbone of pain control techniques in dentistry. Although it is considered one of the painful procedures in daily dental practice, especially for children, however, its obligatory to use LA to eliminate pain during the various dental procedures and maintain child cooperation during the dental session.

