The sample size was calculated based on results obtained from previous studies of similar nature. Sample size was estimated assuming alpha error= 5% and study power= 80%. Tekin et al ⁽³⁶⁾ reported mean \pm SD Sound, Eye and Motor (SEM) score = 3.93 ± 1.223 when intraligamentary anesthesia (ILA) was used, and 5.17 ± 1.891 when inferior alveolar nerve block (IANB) was used. Based on comparison of means, sample size was calculated to be 25 per group, and the total sample size required to compare the effectiveness of CC-ILA technique versus IANB during extraction of primary mandibular molars = number of groups \times number per group= $2 \times 25 = 50$.⁽⁴¹⁾ The sample size was calculated using powerandsamplesize.com calculator.⁽⁴²⁾

Criteria for sample selection:

a) Eligibility Criteria

- Age range from 5 – 7 years.
- Children free of any systemic disease or special health care need (ASA I).⁽⁴³⁾
- No previous bad dental experience.⁽⁴⁴⁾
- Positive or definitely positive behaviour during preoperative assessments according to the Frankl Rating Scale (score 3 or 4) (Appendix I).⁽⁴⁵⁾

- Patients whom their mandibular primary molars are indicated for extraction:^(46, 47)
 - Clinical signs and symptoms of pulp degeneration, such as swelling or sinus tracts.
 - Radiographic evidence of periapical or interradicular radiolucency.
 - Non restorable crowns.
 - Failed pulpotomies.
- Patients whose parents will give their consent to participate.

b) Exclusion Criteria for teeth ⁽⁴⁸⁾

- Root resorption affecting more than one third of the root length.
- Fractured roots due to trauma.
- Signs of mobility.
- Ankylosed roots.
- Active sites of pathosis in area of injection that could affect anaesthetic assessment.
- History of allergy to local anesthesia.

Materials

- a) Topical Anaesthesia – Benzocaine gel 20%.*
- b) 27-guage long anaesthetic needles.**
- b) Local anaesthetic carpules: Articaine hydrochloride 4% with adrenaline 1:100,000.***
- c) Equipment:
 - Wand - STA Single Tooth Anaesthesia Device (Figure 2)****
 - Disposable Wand – STA Handpieces with 30-guage 0.5-inch needles. ****
 - Pulse oximeter.*****
 - Dental anaesthetic syringe (non-disposable breech loading, metallic cartridge type).*****
 - Lower Full-crown Extraction forceps.*****

* Dharma Research, Inc. [name].

** C-K Ject, CK Dental Ind. Co., LTD., Korea.

*** ARTINIBSA, Inibsa Dental S.L.U, [name].

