**** STA; Milestone Scientific, Inc., Livingston, NJ, USA

***** Zacurate, [name].

***** BeehiveSolutionsLtd: [name].

***** Likamed [name].

Figure (2): Wand - STA Single Tooth Anaesthesia Device

Randomization

Participants complying with the inclusion criteria will be randomly assigned using a computer-generated list of random numbers.⁽⁴⁹⁾

Allocation concealment

Each child included in the study will be given a serial number that will be used in the allocation. These numbers will be written in identical sheets of paper with the group to which each child is allocated and placed inside opaque envelopes carrying the respective names of the children.⁽⁵⁰⁾ A trial independent personnel will be assigned to the role of keeping the envelopes and unfolding them only at the time of the local anesthesia injection session so that the group the child is allocated to is concealed from the outcome evaluator.

Grouping

Participants will be randomly and equally allocated to one of the two arms (Figure 1).

- **Group I:** (experimental group n = 25) assigned to CC-ILA.
- **Group II:** (control group n = 25) assigned to conventional injection by IANB.

Blinding

The researcher (operator) who will perform all the injections and extractions as well as record heart rate measurements cannot be blinded to the type of intervention; a second impartial observer (evaluator) will record the Sensory, Eye, Motor (SEM) scale independently.⁽³⁰⁾ The statistician will be blinded to the treatment groups. Since the participants will also be blinded, therefore, the study will be triple-blind.

Examiner reliability

- For standardization, all clinical procedures will be performed by a single operator, who will be trained and calibrated for the Wand – STA system via training sessions by an expert through the manufacturing company, as it is too complex to be applied effectively without more appropriate training. Especially, the coordination between the foot pedal handling and the syringe has shown to be difficult.⁽³³⁾
- Training on heart rate measurement using the pulse oximeter will be also planned.

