Heart rate (HR) is a physiological sign of pain.⁽⁵⁷⁾ It will be measured using a pulse oximeter. A brief demonstration using the pulse oximeter will be done, and the patient will be instructed to stay still and not to move his hands a lot in order to obtain accurate readings. The pulse oximeter will be placed on the patient's index finger to measure the baseline heart rate (before giving the LA), another measurement will be recorded during LA administration, and during extraction. Readings will be recorded at 2-minute intervals and the mean heart rate measurement will be calculated.

B. Objective method:

Sound, Eye, Motor (SEM) Scale (Figure 3), will be used as an objective method for pain assessment during LA administration and extraction. It comprises the following parameters: (1) Sound, (2) Eye, (3) Motor. For each child, the sounds, eye symptoms and body movements will be evaluated independently by a blind impartial observer using the recorded video tapes. The slightest manifestation of the sound, eyes, or motion of the patient is graded in four levels: comfort, mild, moderate, and severe discomfort, and subsequently given grades 1, 2, 3, 4, respectively. SEM score will be calculated by summing the three grades of the parameters. ⁽⁵⁸⁾

Parameter	Comfort	Mild discomfort	Moderate discomfort	Severe discomfort
Grade	1	2	3	4
Sound	No sound	Non-specific sound (probable pain)	Verbal complaint, louder sound	Verbal complaint shouting, crying
Eye	No sign	Dilated eye without tears (anxiety sign)	Tears, sudden eye movements	Crying, tears all over the face
Motor	Relaxed body and hand status	Muscular contraction, contraction of hands	Sudden body and hand movements	Hand movements for defence, turning the head to the opposite side

Figure (3): SEM scale for the assessment of children's behaviour

Subjective method:

A modified face scale⁽⁵⁹⁾ (Figure 4) from the Maunuksela et al⁽⁶⁰⁾ scale will be used to subjectively record pain during LA injection and extraction. It consists of three schematic faces with different facial expressions for happy and sad faces representing: (A) satisfaction; (B) indifference; and (C) dissatisfaction, respectively. Each child will be trained to use the scale by modelling and then asking each participant to think of the last time she/he felt something painful and to select the facial expression that best represented his/her experience of discomfort.

[figure not shown]

Figure (4): Faces scale modified from the Maunuksela et al scale.

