(A) satisfaction; (B) indifference; and (C) dissatisfaction

II. Assessment of occurrence of adverse events

Parents will be recalled after 24 hours following extraction during follow-up phone calls. Recovery parameter questions will be asked to ascertain the occurrence of lip and cheek biting, post-operative pain, or any adverse events.

STATISTICAL ANALYSIS

All data will be collected; descriptive quantitative values will be summarised using mean and standard deviation, while count and percentage will be used for qualitative values. The data will be represented by suitable tables and graphs. Comparing between normally distributed data will occur using T- and Paired T-tests, while for not – normally distributed data, Wilcoxon signed-rank and Mann-Whitney U tests will be used.

All statistical analyses will be performed with statistical Package for Social Sciences* (SPSS) software version 21.⁽⁶¹⁾ The significance level will be set at $P < 0.05$.

*SPSS Inc., Version 21.0, Chicago, IL, USA

ETHICAL CONSIDERATIONS

The study will be conducted following the ethical principles for medical research involving human subjects in Declaration of Helsinki.⁽⁶²⁾ Ethical approval will be obtained from the Research Ethics Committee, Faculty of Dentistry, Alexandria University before commencing the study.

The objectives, risks and benefits of the study will be explained to parents/ guardians and a signed informed consent will be obtained prior to treatment. (Appendix II). Verbal consent will be obtained from the children before the intervention.

Parents and children will be given age-appropriate oral hygiene instructions including proper teeth brushing twice a day especially before bedtime, as well as flossing if indicated. These measures will be demonstrated on a model. A fluoridated toothpaste and a brush will be provided to each participant on the day of the treatment.

All needed treatment will be provided to the child including any restorations, space maintainers and fluoride application. Post extraction instructions will be explained well to the parents and patients to ensure good wound healing. All the possible clinical and/or adverse outcomes will be explained to the parents and they will be asked to report immediately if any of them occurs.

PROBLEMS ANTICIPATED

1. Lack of compliance from patients and/or their parents.
2. Drop – out of patients during the follow up period.
3. Difficulty in collecting the proposed sample.

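### Baseline heart rate is recorded in every child but no listed between-arm test uses it; baseline-adjusted versions of both listed tests would gain precision at small cost

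*Combined protocol and SAP*

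**What the plan says.** The Abstract states: "Heart rate will be used as vital parameter of pain, and will be recorded at base line, during injection and during extraction procedure". Under Study Outcomes, the physiologic method uses a pulse oximeter "to measure the baseline heart rate (before giving the LA), another measurement will be recorded during LA administration, and during extraction". It adds: "Readings will be recorded at 2-minute intervals and the mean heart rate measurement will be calculated".

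The Statistical Analysis section is the whole analysis plan. For normal data: "Comparing between normally distributed data will occur using T- and Paired T-tests". For non-normal data: "Wilcoxon signed-rank and Mann-Whitney U tests will be used". It assigns no test to heart rate and names no covariate, regression model or change from baseline.

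The design has two parallel arms: "Participants will be randomly and equally allocated to one of the two arms". The sample size rests on the SEM score: "Based on comparison of means, sample size was calculated to be 25 per group". SEM "will be used as an objective method for pain assessment during LA administration and extraction", so it has no baseline reading.

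**The concern.** The paired t-test and the signed-rank test work within a child and do not compare arms. That leaves the two-sample t-test and Mann-Whitney U, neither of which takes a covariate. Either could be run on the phase value, which ignores baseline, or on the change from baseline, which fixes the baseline slope at 1. The plan does not say which.

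Which is more precise depends on the baseline/phase correlation and on the ratio of the two standard deviations, and the documents give neither. ANCOVA estimates the slope from the data, so it needs no guess. At stake is the precision of one of three pain measures, and a choice between phase value and change that is open until the data are seen.

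**Working it through.** **The plan's own figure.** Inputs from Sample size estimation: SEM 3.93 (SD 1.223) against 5.17 (SD 1.891), difference 1.24, alpha 5%, power 80%; two-sided testing is assumed. n per group = 2(1.96 + 0.842)² × SD² / 1.24². The mean SD, 1.557, gives 25; the root-mean-square SD, 1.592, gives 26. The stated 25 reproduces, and heart rate plays no part in it.

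**ANCOVA against the unadjusted t-test, normal data.** N = 50. The documents give no heart-rate effect, SD or correlation (ρ), so starting powers of 50% and 80% and ρ from 0 to 0.7 are assumed. These powers correspond to noncentrality 2.000 and 2.859 on 48 df, or differences of 0.566 and 0.809 phase SDs.

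Expected variance ratio, ANCOVA to t-test = (1 − ρ²)(1 + 1/(N − 4)) = (1 − ρ²)(47/46). Dividing the noncentrality by the square root of this ratio and using 47 df gives:

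| ρ | Variance ratio | Power from 50% | Power from 80% |
|---|---|---|---|
| 0 | 1.022 | 49.1% | 79.1% |
| 0.2 | 0.981 | 50.7% | 80.7% |
| 0.3 | 0.930 | 52.9% | 82.7% |
| 0.5 | 0.766 | 60.9% | 89.2% |
| 0.7 | 0.521 | 77.4% | 97.2% |

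For example, at ρ = 0.5: 2.000/√0.766 = 2.285, hence 60.9%.

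The variance breaks even at ρ = √(1/47) = 0.146; allowing for the lost degree of freedom in the interval gives 0.150. At ρ = 0 the power loss peaks at 0.95 points, where the t-test has 70% power. The 95% CI width relative to the unadjusted one is 1.011, 0.965, 0.876 and 0.722 at ρ = 0, 0.3, 0.5 and 0.7. Simulation (40,000 trials per ρ, 80% start) agrees: ANCOVA 79.0%, 82.8%, 89.2% and 97.3% at the same four values. With 20 evaluable children per arm, break-even is 0.164 to 0.170 and the cost at most about 1.2 points.

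**The t-test on change from baseline.** Variance factor = 1 + 1/k² − 2ρ/k, where k = phase SD/baseline SD. Power from a 50% start:

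| k | ρ = 0 | 0.3 | 0.5 | 0.7 |
|---|---|---|---|---|
| 1 | 28.3% | 38.1% | 50.0% | 71.6% |
| 1.5 | 37.1% | 48.3% | 60.3% | 78.3% |
| 2 | 41.8% | 52.0% | 61.9% | 75.3% |

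Against the better of the two listed t-tests, over ρ 0 to 0.8 and k 0.75 to 2, ANCOVA's largest shortfall is 1.0 point (ρ = 0.5, k = 2: 61.9 − 60.9).

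**Non-normal data.** Here the plan's between-arm test is Mann-Whitney, so that is the comparison needed. Simulated power with 25 per arm and a shift of 0.566 SD (Mann-Whitney and ANCOVA from one set of runs, 20,000 trials per cell; Quade from a separate set, 40,000 per cell):

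| Shape | ρ | Mann-Whitney | ANCOVA | Quade |
|---|---|---|---|---|
| Exponential | 0 | 76.7% | 52.7% | 76.7% |
| Exponential | 0.3 | 70.7% | 55.4% | 74.9% |
| Exponential | 0.5 | 65.3% | 63.7% | 76.3% |
| Exponential | 0.7 | 62.8% | 78.3% | 84.3% |
| t, 4 df | 0 | 62.4% | 53.2% | 61.6% |
| t, 4 df | 0.3 | 59.7% | 56.1% | 64.0% |
| t, 4 df | 0.5 | 57.9% | 64.3% | 69.2% |

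Ordinary ANCOVA is 76.7 − 52.7 = 24.0 points below Mann-Whitney for exponential data at ρ = 0, and break-even moves to about ρ = 0.5. A Shapiro-based switch between t-test and Mann-Whitney, one reading of the plan, gives 75.8% and 70.4% for exponential data at ρ = 0 and 0.3, so the plan's route would keep most of that power. Quade is within 1 point of Mann-Whitney at ρ = 0 and above it from 0.3. Type I error under these shapes is 4.6% to 4.9% for ANCOVA; for Quade it is 4.8% to 5.3%.

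**Timing of the baseline.** Three sections bear on it. Allocation concealment has the envelope opened at the injection session. Psychological child preparation gives the two groups different scripts. Blinding says the unblinded operator records heart rate. Baseline is defined only as preceding the anaesthetic, so the text allows it to follow both the envelope and the script.

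**The case against.** The strongest objection is that this is a preference. The listed tests are valid, heart rate is one of three pain measures, and every gain rests on an assumed correlation. Gains above 10 points from a 50% start need ρ of about 0.5 or more, which the documents neither support nor exclude. The plan's t-test could also be run on change scores, which nearly match ANCOVA from ρ = 0.5 when the phase SD is 1.5 times the baseline SD. All of this stands, and it limits the point to efficiency. It does not remove it: at equal SDs the change score is 77.4 − 71.6 = 5.8 to 49.1 − 28.3 = 20.8 points below ANCOVA over ρ 0 to 0.7, and the plan gives no basis for choosing between change and phase value.

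A second objection is that making ordinary ANCOVA the main analysis whatever the distribution would discard the plan's Mann-Whitney route and could lose far more than 1 point. That is correct, and the fix therefore keeps the split.

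A third is that a baseline taken after allocation is known could be affected by it. ANCOVA and change scores could then be biased where a phase-value test is not. This also stands, as a condition on the fix.

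**Conclusion.** The point holds as a worthwhile, inexpensive improvement to the heart-rate analysis. With 25 per arm and roughly normal data, ANCOVA beats the unadjusted t-test above ρ of about 0.15 and costs about 1 point of power at most against the listed t-tests. Those two figures depend on the number of children and on approximate normality with a common slope. The size of any gain depends on a correlation that must be assumed.

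A reader might infer three stronger things that the documents do not support:

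- That the unadjusted comparison is biased or invalid. Allocation is random, and the standard error of the t-test already covers chance baseline imbalance.
- That the trial's sample size or power is affected. It was set on SEM, which has no baseline reading.
- That adjustment can never cost more than about 1 point. The plan sends non-normal data to Mann-Whitney, and against that test ordinary ANCOVA can be up to about 24 points lower in the cells computed. The exponential and t shapes are assumptions too; the documents say nothing about the distribution of heart rate.

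**What to change.** Add to Statistical Analysis:

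> Heart rate during injection and heart rate during extraction (each the mean of the readings in that phase, excluding baseline) will each be compared between arms with baseline heart rate as covariate. Where the data are treated as normal, ANCOVA on randomised group replaces the two-sample t-test, and the adjusted mean difference with its 95% CI is reported. Where they are not, rank-based (Quade) ANCOVA with the same covariate replaces Mann-Whitney U. Within-arm paired tests are descriptive.

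Add to the physiologic method: the baseline reading used as covariate is taken before the allocation envelope is opened and before the group-specific preparation script.

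The cost is a few sentences, one degree of freedom, about 1 point of power if ρ is near zero, and fixing the order of the baseline reading. No extra data or visits are needed.

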59. Pierro VSdS, Barcelos R, de Souza IPR, Raymundo Jr R. Pediatric bitewing film holder: preschoolers' acceptance and radiographs' diagnostic quality. *Pediatr Dent*. 2008;30:342-7.
61. SPSS I. Statistical package for the social sciences. Data analysis software packages Version. 2012;21.
62. World Medical A. World Medical Association Declaration of Helsinki. Ethical principles for medical research involving human subjects. *Bull World Health Organ*. 2001;79:373-4.

EFFECTIVENESS OF COMPUTER - CONTROLLED INTRALIGAMENTARY LOCAL ANAESTHESIA IN EXTRACTION OF MANDIBULAR PRIMARY MOLARS (RANDOMISED CONTROLLED CLINICAL TRIAL)

Name: [name]

Summary Statement

Sample size was estimated assuming alpha error= 5% and study power= 80%. Tekin et al.⁽¹⁾ reported mean \pm SD Sound, Eye and Motor (SEM) score = 3.93 ± 1.22 when intraligamentary anesthesia (ILA) was used, and 5.17 ± 1.89 when inferior alveolar nerve block (IANB) was used. Based on comparison of means, sample size was calculated to be 25 per group, and the total number required to compare the effectiveness of computer-controlled ILA technique versus IANB during extraction of primary mandibular molars = number of groups \times number per group = $2 \times 25 = 50$.⁽²⁾

Software

[figure not shown]
<http://powerandsamplesize.com/Calculators/Compare-2-Means/2-Sample-Equality>.

References

[name]; B.D.S, M.Sc, Ph.D

Professor of Dental Public Health
Alexandria University
Wednesday, January 20, 2021

IRB NO: 00010556 – IORG 0008839
<https://ohrp.cit.nih.gov/search/search.aspx>

كلية طب الاسنان
 FACULTY OF DENISTRY
 كليته معتمدة

Ethical Guidelines for Conduct of Research on Human Subject

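### The SEM comparison is valid but unadjusted; prespecifying adjustment for the Frankl score, already required at screening, is a cheap improvement with a modest, uncertain gain in power

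*Combined protocol and SAP*

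**What the plan says.** The Statistical Analysis section gives the whole inferential plan. For data judged normal, "Comparing between normally distributed data will occur using T- and Paired T-tests"; otherwise Wilcoxon signed-rank and Mann-Whitney tests are used. No covariate, regression model or confidence interval is mentioned.

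The Randomization section describes a computer-generated list without a stratification factor. Under Grouping, "Participants will be randomly and equally allocated to one of the two arms".

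The Eligibility Criteria require "Positive or definitely positive behaviour during preoperative assessments according to the Frankl Rating Scale (score 3 or 4". Each enrolled child therefore has a two-level behaviour rating before treatment. The tooth is examined and radiographed at the screening visit, but nothing says that first versus second primary molar will be recorded as data.

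The sample size rests on SEM: "3.93 ± 1.223 when intraligamentary anesthesia (ILA) was used" and "5.17 ± 1.891 when inferior alveolar nerve block (IANB) was used". It concludes: "Based on comparison of means, sample size was calculated to be 25 per group". The stated alpha is 5% and the stated power 80%.

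**The concern.** SEM grades sound, eye signs and body movement, and its figure presents it as a scale of children's behaviour. Frankl rates the child's cooperation before treatment. It is plausible, though the documents do not show it, that a child rated 3 will score higher on SEM than a child rated 4 whatever the injection technique. If so, that variation stays in the error term of a two-group test, and neither the allocation nor the analysis deals with a chance difference in Frankl mix between the arms.

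Two things are at stake, both modest. One is some precision in a 50-child trial whose power is at or slightly below its target. The other is the credibility of any later adjustment: a covariate chosen after the data are seen invites the suspicion of selection, and one named in advance does not.

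**Working it through.** **Inputs.** From Sample size estimation: means 3.93 and 5.17, so a difference of 1.24; SDs 1.223 and 1.891; 25 per arm; alpha 5%; target power 80%. Two-sided testing is inferred from the two-sample equality calculator that the plan cites. R-squared of Frankl with SEM is not in the documents and is assumed over 0 to 0.20.

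**1. The plan's own figure.** n per arm = 2 × [SD × (1.960 + 0.842) / 1.24]².
- Simple mean of the SDs, (1.223 + 1.891)/2 = 1.557: n = 24.75, so 25. The stated figure reproduces.
- Pooled SD, √[(1.223² + 1.891²)/2] = 1.592: n = 25.89, so 26.

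**2. Unadjusted power at 25 per arm.**

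| Formula | SD 1.557 | SD 1.592 |
|---|---|---|
| Normal approximation | 80.4% | 78.6% |
| t test, 48 df | 78.8% | 77.0% |

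The gap to 80% therefore runs from none to about 3 points. By the t test with the pooled SD, 80% needs 27 per arm, or 4 more children.

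**3. Power adjusted for Frankl alone.** Noncentrality = 1.24 / {1.592 × √(1 − R²) × √[(2/25)(1 + 1/47)]}, on 47 df. The factor 1 + 1/47 allows for chance imbalance in one covariate. I checked this by simulation (40,000 trials per setting, normal errors, the plan's unequal SDs, Frankl split 50/50 by assumption, HC1 standard errors).

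| Assumed R² | Noncentrality | Power, formula | Power, simulation |
|---|---|---|---|
| 0 | 2.724 | 76.1% | 76.3% |
| 0.05 | 2.795 | 78.2% | 77.8% |
| 0.10 | 2.872 | 80.3% | 80.2% |
| 0.20 | 3.046 | 84.7% | 84.8% |

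Unadjusted power in the same simulations was about 77% throughout. A separate simulation run put the R² = 0.10 case nearer 82%; I use the lower value because the formula supports it. The ordinary model-based standard error gave the same power as HC1 to within 0.2 points.

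**4. What 80% requires.** Solving step 3 for 80% gives R² = 0.093, or 0.074 without the imbalance factor. For a two-level factor split evenly, the SEM gap between levels is 2 × 1.592 × √R². That is 0.87 at 0.074 and 0.97 at 0.093, against an assumed treatment difference of 1.24.

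**5. Cost if the covariates are unrelated to SEM (R² = 0, simulation).**

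| Model | HC1 | HC3 |
|---|---|---|
| Frankl | 76.3% | 74.3% |
| Frankl and molar type | 75.1% | 72.2% |

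Against about 77% unadjusted, the loss is about 1 point for Frankl with HC1, and roughly 2 to 5 points once molar type, HC3 or both are added.

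**6. Chance imbalance.** If Frankl splits 50/50, the two arm counts are independent Binomial(25, 0.5). The probability that they differ by 5 or more children is about 20%.

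**The case against.** The strongest reply is that nothing here is wrong. In a randomised trial the unadjusted comparison is unbiased, its standard error already covers chance imbalance, and it matches the comparison of means behind the sample size. That stands in full, and it is why this is an improvement and not a correction.

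A reader might infer that the trial is underpowered and that adjustment would repair it. The documents do not support that. The 25 per group reproduces, the shortfall is 0 to 3 points depending on the formula, and the gain rests on an R-squared that nobody has supplied. Eligibility leaves only the two cooperative Frankl categories, which limits what the score can explain, and a gap of nearly one SEM point between them would be needed to reach 80%.

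Nor is adjustment the only route without more children. For example, the Abstract has two investigators scoring SEM where the Blinding section has one observer; averaging two ratings might also reduce error. A reader might further assume that molar type is ready for use. It is knowable from screening, but it is not listed as a recorded variable and nothing in the documents links it to SEM.

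Finally, SEM is an integer sum with a floor of 3 and the assumed intraligamentary mean is 3.93, so skew is likely and the Mann-Whitney branch may apply. The power figures above assume normal errors and are approximate for that reason. It also means that an adjusted model must replace the normality-driven choice of test as primary, not sit beside it.

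**Conclusion.** The point holds as an optional, low-cost improvement. The analysis ignores a pre-treatment behaviour score that screening must produce, while the outcome is a behaviour score. Adjusting for Frankl alone changes power by about −1 point if it is unrelated to SEM, and by about +1, +3 and +8 points at assumed R-squared of 0.05, 0.10 and 0.20. These figures rest on the plan's difference and SDs, normal errors, an even Frankl split and no lost SEM data. Imbalance of 5 or more children has a material chance, about one in five under that split, but it is not likely. The case for prespecifying rests as much on settling one estimate with an interval in advance as on power.

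**What to change.** Before SEM is analysed by arm, add to the Statistical Analysis section that the primary analysis of SEM at extraction is a linear model with arm and Frankl score (3 v 4). Name the standard error, for example HC1, and report the adjusted mean difference with its 95% confidence interval. State that this replaces the normality-based choice of test for that outcome, and keep the unadjusted t or Mann-Whitney test as a sensitivity analysis.

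Make sure that the individual Frankl score, not only eligibility, reaches the data file. Include molar type only if first versus second molar is added as a recorded field, and accept its small cost in power if it proves unrelated to SEM. Confirm that the planned SPSS version produces the named standard error; the model-based one would serve almost equally well under the inputs above.

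The cost is a few sentences, no extra children or visits, and about 1 point of power if Frankl turns out not to matter.
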